# 1. Introduction

# 1.1. Background and rationale

Several important licensed and investigational vaccines have lower efficacy, and induce impaired immune responses, in low-income countries (LICs) compared to high-income countries and in rural, compared to urban, settings. Understanding these population differences is crucial for informing strategies towards optimisation of vaccine effectiveness in the tropics. We hypothesise that malaria infection suppresses immune responses to unrelated vaccines, and that this effect can be reversed, at least in part, by monthly preventive treatment of malaria in schools in high transmission settings.

To address this hypothesis, POPVAC B trial is being carried out among adolescents in rural sub-counties of Jinja district, Uganda to assess if monthly preventive treatment of malaria with dihyrodartemisinin-piperaquine (DP) will impact on vaccine responses in this population.

# 1.2. Research Objectives and hypothesis

# Study objectives

The primary objective of this trial is to determine whether there are reversible effects of malaria infection on vaccine responses in adolescents, using an intervention study.

# Secondary objectives are:

- a) To determine effects on correlates of protective immunity (where recognised correlates exist).
- b) To determine effects on vaccine response waning.
- c) To determine whether there are differential effects on priming vs boosting immunisations.
- d) To determine effects on current malaria infection prevalence and intensity.

The exploratory objective is to explore immunology among subsets of participants to further characterise effects of preventive treatment of malaria on vaccine responses.

# Primary objective hypothesis

The null hypothesis is that there is no difference in the mean responses induced by BCG, YF-17D, Ty21a, HPV and Td vaccines between adolescents who received monthly DP and placebo treatment. The alternative hypothesis is that the mean vaccine responses will differ between adolescents receiving monthly DP and placebo treatment.

# 2. Study Methods

# 2.1. Trial design

This trial is a randomised, double-blind, placebo-controlled, parallel group trial comparing effect of monthly preventive treatment of malaria with dihyrodartemisinin-piperaquine (DP) versus placebo on vaccine response outcomes. Treatment allocation is a 1:1 ratio for the trial intervention.

#### 2.2. Sample size considerations

The original target sample size was 640 healthy adolescents (320 in each arm) of whom 60% (384) were expected to have malaria infection at the outset will be enrolled into the trial. This target sample size was informed by the expected difference in vaccine responses between the two arms, with full details of sample size considerations presented in the protocol. However, due to the onset of the COVID-19 pandemic and the consequent restrictions in Uganda, it was not possible to achieve the original target sample size. Table 1 shows updated power estimation for the achieved sample size of 341.

Table 1. Updated power estimates for the primary analysis population of participants with
malaria infection at baseline (5% significance level): n=341, assuming 60% malaria
neoral and allowing for 200/ less to follow up

	Log 10 difference						
Standard deviation (log 10 )	0.10	0.12	0.14	0.16	0.18	0.20	
102 DP vs 102 placebo (baseline malaria infected only), 20% loss to follow-up, i.e. analysis based on 82 vs 82							
0.3	56%	72%	84%	92%	97%	99%	
0.4	36%	48%	61%	72%	82%	89%	
0.5	25%	33%	43%	53%	63%	72%	
0.6	19%	25%	32%	40%	48%	56%	
Cells highlighted in arey correspond to >80% nower							

prevalence, and allowing for 20% loss to follow-up

#### 2.3. Randomisation

Eligible volunteers who consent will be enrolled and allocated sequentially to one of the two trial arms according to the randomisation code. The randomisation code was generated using a randomly permuted block size and will be used to allocate participants to either receive monthly DP (DP arm) or placebo (placebo arm).

#### 2.4. Blinding

The trial is double blinded and will remain so until all data has been collected, cleaned, and analysed.

# 2.5. Statistical interim analyses and stopping guidance

Analyses will be conducted for safety reviews as outlined in the Data Safety Monitoring Board (DSMB) charter. For each safety analysis, the DSMB members will review data on trial progress and adverse events. Details of the safety holding rules are detailed in the protocol. Since recruitment will be conducted over a short time, there is no statistical interim analysis planned for comparison of vaccine responses between the two arms.

# 2.6. Timing for the primary outcome analysis

Analysis for comparison of each of the vaccine responses between the two trial arms will take place after enrolment of all participants in the two arms has been completed and samples for assessing the primary outcomes have been taken, laboratory assays for that particular vaccine primary outcome have been conducted and the data have been entered and cleaned.

# 2.7. Timing of outcome assessment

In the following section, week numbers in brackets are based on the schedule in the protocol, with BCG immunisation given at week 0, and YF-17D, Ty21a and first dose of HPV given at week 4 and second dose of HPV and Td given at week 28.

### Timing of primary outcomes

BCG: BCG-specific IFN- $\gamma$  ELIspot response eight weeks post BCG immunisation (week 8)

*YF-17D*: neutralising antibody titres (plaque-reduction neutralisation test) at four weeks post YF immunisation (week 8).

*Ty21a*: *Salmonella typhi* lipopolysaccharide (LPS)-specific immunoglobulin (Ig)G concentration at four weeks post Ty21a immunisation (week 8).

*HPV*: IgG specific for L1-proteins of HPV-16/18 at four weeks post HPV priming immunisation (week 8).

*Td*: tetanus and diphtheria toxoid-specific IgG concentration at 24 weeks post Td immunisation (week 52).

### Timing of secondary outcomes

*Protective immunity:* Proportions with protective neutralising antibody (YF), i.e. neutralising antibody>1/5; protective IgG levels (TT), i.e. IgG>0.1 IU/ml; seroconversion rates (Ty21a) at four weeks post the corresponding immunisation (week 8).

*Response waning:* Primary outcome measures for all vaccines repeated at week 52 except for Td whose primary outcome responses are measured at week 52.

*Priming versus boosting:* HPV vaccine responses four weeks after the priming dose (week 8) and 24 weeks after the boosting dose (week 52).

Current malaria infection status and intensity at screening (week -8), weeks 0, 4, 8, 52.

# 3. Statistical Principles

# 3.1. Level of statistical significance

All applicable statistical tests will be 2-sided. All tests will be performed using a 5% significance level. 95% confidence intervals will be presented.

# 3.2. Compliance and Protocol Deviations

Compliance to the protocol schedule will be assessed based on the percent of participants who have attended the scheduled visits and received the appropriate assigned treatments and vaccines within the permitted time windows around the vaccinations and sample collection visits as specified in the schedule of visits and procedures in the protocol.

# 3.3. Analysis population

The primary analysis will be done on participants who are infected with malaria at baseline (based on the result of a malaria PCR test) to investigate the effect of parasite removal. The secondary analysis will include all randomised individuals. For all responses to vaccines, analysis will be done by intention to treat (ITT), that is, participants will be included in the arm to which they were randomised, regardless of whether they have received all allocated DP/Placebo treatments.

# Analysis population for the primary outcomes

*BCG-specific IFN-* $\gamma$ *ELIspot:* The analysis population for BCG-specific *IFN-* $\gamma$ *ELIspot* response will include all enrolled participants who receive BCG at week 0 and have BCG-specific IFN- $\gamma$  ELIspot response measurement at week 8.

*YF-17D:* The analysis population for YF-17D vaccine response will include all enrolled participants who receive yellow fever vaccine at week 4 and have YF-17D response measurement at week 8.

*Ty21a:* The analysis population for Typhoid vaccine (Ty21a) response will include all enrolled participants who receive Typhoid vaccine (Ty21a) at week 4 and have YF-17D response measurement at week 8.

*HPV:* The analysis population for HPV vaccine response will include all enrolled participants who receive HPV vaccine at week 4 and have HPV response measurement at week 8.

*Td:* The analysis population for Td vaccine response will include all enrolled participants who receive Tetanus and diphtheria vaccine at week 28 and have Td response measurements at week 52.

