# Analysis population for the secondary outcomes

*Protective immunity:* Analysis population for YF, Ty21a and Td protective immunity will include all enrolled participants who receive the respective vaccine (YF-17D, Ty21a at week 4, Td vaccine at week 28) and have responses to the respective vaccines at 4 weeks post vaccination for YF-17D, Ty21a and 24 weeks post Td vaccination.

*Response waning:* Analysis population will include all enrolled participants who receive any of BCG, YF-17D, Ty21a, HPV and Td vaccines; have corresponding responses to any of these vaccines at weeks 8, 28 (for Td vaccine) and 52 post vaccination.

*Priming versus boosting:* Analysis population will include all enrolled participants who receive a priming dose of HPV vaccine at week 4 and a boosting dose at week 28 and have corresponding responses to the vaccine (at weeks 8 and 52).

Current malaria infection status and intensity: Analysis population will include all enrolled participants who have serum/plasma samples and corresponding results at any of these time points; baseline (week -8), on immunisation days (weeks 0, 4, 8 and 28), and on primary (weeks 8 and 52) and secondary endpoint days (week 52).

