# 5.3. Missing data

Participants with missing data on BCG, YF-17D, Ty21a, HPV and Td vaccination and/or measurement for primary endpoints will be excluded from the respective analysis as detailed in the analysis population section. There will be no imputation of missing data.

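### The Ty21a primary analysis set is defined by having a yellow fever result instead of a Ty21a result; the effect may be nil, but the rule should be corrected before unblinding

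*SAP*

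**What the plan says.** SAP section 3.3, under the heading on analysis populations for the primary outcomes, defines a separate set for each vaccine. For Ty21a the set is enrolled participants "who receive Typhoid vaccine (Ty21a) at week 4 and have YF-17D response measurement at week 8".

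Section 2.7 gives the Ty21a primary outcome as *Salmonella typhi* "lipopolysaccharide (LPS)-specific immunoglobulin (Ig)G concentration at four weeks post Ty21a immunisation (week 8"). Section 5.1.1 lists the same outcome.

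Section 5.3 says that participants lacking the vaccination or the primary-endpoint measurement "will be excluded from the respective analysis as detailed in the analysis population section", and that nothing will be imputed.

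**The concern.** An analysis set for a primary outcome should depend on having that outcome. Here it depends on another vaccine's assay. A participant who received Ty21a and has a valid LPS IgG result could be left out only because the yellow fever titre is missing. That discards usable outcome data and adds a second post-randomisation condition that has nothing to do with the typhoid response. The count of exclusions from the primary analysis, which section 4.1 asks for with reasons, would then record a reason that makes no sense for Ty21a.

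The text at fault is the operative definition for one of the five vaccines in the primary objective. An analyst who follows it gets the wrong set if the two assays are missing in different people. An analyst who quietly ignores it departs from the SAP without a record.

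**Working it through.** **Step 1. Compare the definitions in section 3.3.** The yellow fever set is those "who receive yellow fever vaccine at week 4 and have YF-17D response measurement at week 8". The HPV set is those "who receive HPV vaccine at week 4 and have HPV response measurement at week 8". The BCG and Td sets follow the same pattern: own vaccine, own measurement. Only the Ty21a line pairs a vaccine with another vaccine's measurement, and it repeats the measurement condition of the yellow fever line just above it.

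**Step 2. Confirm that the two measurements differ.** Section 2.7 gives the yellow fever outcome as "neutralising antibody titres (plaque-reduction neutralisation test) at four weeks post YF immunisation (week 8"). The Ty21a outcome is an LPS-specific IgG concentration. One result does not imply the other.

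**Step 3. Look for a correction elsewhere.** For the secondary protective-immunity outcomes, section 3.3 requires that participants "have responses to the respective vaccines at 4 weeks post vaccination for YF-17D, Ty21a". This shows the intent but governs only the secondary outcome. Read literally, the two week-8 Ty21a comparisons would use sets with different entry conditions. Section 5.3 excludes people without the endpoint, but nothing in it restores someone whom section 3.3 has left out.

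**Step 4. Apply the rules to the four possible cases**, among participants who received Ty21a at week 4:

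| Week-8 LPS IgG | Week-8 YF titre | Section 3.3 as written | After section 5.3 | Set matching the outcome |
|---|---|---|---|---|
| present | present | in | in | in |
| present | absent | out | out | **in** |
| absent | present | in | out | out |
| absent | absent | out | out | out |

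Only the second row ends up wrong.

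**Step 5. Size.** The SAP does not say how many participants fall in the second row. To show the scale, start from Table 1 in section 2.2.

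- Planned number per arm: 341 × 0.6 / 2 = 102.3, taken as 102; then 102 × 0.8 = 81.6, taken as 82.
- Power, two-sided 5%, normal approximation: Φ(δ / (σ√(2/n)) − 1.96).
- With n = 82, σ = 0.4 and δ = 0.18: 0.4 × √(2/82) = 0.0625; 0.18 / 0.0625 = 2.88; Φ(2.88 − 1.96) = 82.2%. Table 1 gives 82%, so the figure is reproduced.

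Now let m be the share of those with an LPS IgG result who lack a yellow fever titre, so that n = 82(1 − m). The values of m are assumptions.

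| m | n per arm | Power, SD 0.4, difference 0.18 | Power, SD 0.3, difference 0.14 |
|---|---|---|---|
| 0 | 82 | 82.2% | 84.8% |
| 2% | 80.4 | 81.4% | 84.1% |
| 5% | 77.9 | 80.2% | 83.0% |
| 10% | 73.8 | 78.0% | 80.9% |
| 20% | 65.6 | 73.1% | 76.2% |

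These losses would come on top of the 20% already allowed for in Table 1.

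**The case against.** The strongest reply is that this is an obvious copying slip. The parallel definitions, the wording for the secondary outcomes and the reference in section 5.3 to the respective analysis all show what was meant, and a careful analyst would use LPS IgG. Both assays belong to week 8, so a missed visit removes both results and the two sets may coincide. All of this stands, and it limits the severity. It does not make the written rule right: the rule defines a primary-outcome set, and the correct reading has to be inferred from other text.

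Three stronger readings are tempting, but the SAP does not support them.

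- *People without an LPS IgG result would be counted in the Ty21a analysis.* They meet the section 3.3 wording, but section 5.3 excludes anyone missing the primary-endpoint measurement, and they have no value to enter in a t test.
- *The reference to all enrolled participants in each definition contradicts the restriction to malaria-infected participants.* Section 3.3 opens with the governing statement: "The primary analysis will be done on participants who are infected with malaria at baseline". It then names all randomised individuals for the secondary analysis. The vaccine-specific definitions add conditions beneath that and can serve both analyses.
- *The Ty21a comparison loses material power.* That needs a sizeable m. The SAP gives no value, and m = 0 is quite possible.

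**Conclusion.** The point holds in a narrow form. The Ty21a primary analysis set is tied to the wrong assay, and no other text in the SAP overrides this. The one real consequence of literal use is the exclusion of participants with an LPS IgG result but no yellow fever titre.

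The size is unknown and may be nil. It rests entirely on how far missingness differs between the two week-8 assays, and the power figures above are illustrations of that assumption, not estimates. Table 1 and every other stated number stay as they are, as do the test and the other four primary-outcome sets. Because the intent is clear and the slip affects one definition, this is a minor to should-fix correction.

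**What to change.** In section 3.3, rewrite the measurement condition of the Ty21a primary definition so that the set is those given Ty21a at week 4 who have an *S. typhi* LPS-specific IgG result at week 8. Make the change before unblinding and record it as a correction to the SAP.

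The cost is one phrase of SAP wording. No new data, assay, sample size calculation or change of method is needed.

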# Analysis population for the secondary outcomes

*Protective immunity:* Analysis population for YF, Ty21a and Td protective immunity will include all enrolled participants who receive the respective vaccine (YF-17D, Ty21a at week 4, Td vaccine at week 28) and have responses to the respective vaccines at 4 weeks post vaccination for YF-17D, Ty21a and 24 weeks post Td vaccination.

*Response waning:* Analysis population will include all enrolled participants who receive any of BCG, YF-17D, Ty21a, HPV and Td vaccines; have corresponding responses to any of these vaccines at weeks 8, 28 (for Td vaccine) and 52 post vaccination.

*Priming versus boosting:* Analysis population will include all enrolled participants who receive a priming dose of HPV vaccine at week 4 and a boosting dose at week 28 and have corresponding responses to the vaccine (at weeks 8 and 52).

Current malaria infection status and intensity: Analysis population will include all enrolled participants who have serum/plasma samples and corresponding results at any of these time points; baseline (week -8), on immunisation days (weeks 0, 4, 8 and 28), and on primary (weeks 8 and 52) and secondary endpoint days (week 52).

# 4. Trial population

# 4.1. Screening, eligibility, recruitment and lost to follow up of participants.

A CONSORT flow diagram will be used to summarise the number of participants in each trial arm who were:

assessed for eligibility at screening • ineligible at screening\* • eligible and randomised • received vaccines • did not receive vaccines\* • lost to follow-up\* • included in the primary analysis • excluded from the primary analysis\*

\*reasons for these events will be provided.

# **CONSORT Flow Diagram**

Note: Details of inclusion and exclusion criteria are listed in the protocol

# 4.2. Baseline characteristics

Participants will be described with respect to their baseline characteristics including age, sex, school, location of birth, prior vaccination status, malaria infection status both overall and separately for each arm.

Categorical variables will be summarised by numbers and percentages. Continuous variables will be summarised by mean, SD and range if data are normal or median, IQR and range if data are skewed. No statistical tests will be done to compare baseline characteristics between arms.

# 5. Analysis of outcomes

# 5.1. Outcome definitions

Timing for the outcome assessments is described in section 2.7

### 5.1.1. Outcomes for primary objective

- BCG: BCG-specific IFN-γ ELIspot response
- *YF-17D:* neutralising antibody titres
- *Ty21a: Salmonella typhi* lipopolysaccharide (LPS)-specific immunoglobulin (Ig)G concentration
- *HPV:* IgG specific for L1-proteins of HPV-16/18 at four weeks post HPV priming immunisation
- *Td:* tetanus and diphtheria toxoid-specific IgG concentration

### 5.1.2. Outcomes for secondary objective

- *Protective immunity:* Proportions with protective neutralising antibody (YF), i.e., >1/5; protective IgG levels (TT), i.e., >0.1 IU/mL; seroconversion rates (Ty21a).
- *Response waning:* Primary outcome measures for all vaccines repeated at week 52.
- Priming versus boosting: IgG specific for L1-proteins of HPV-16/18.
- Current malaria infection status and intensity: Infection status (infected and uninfected) and intensity (light, medium and heavy).

### 5.2. Analysis methods

### 5.2.1. Analysis of primary objective outcome measures

Unpaired t tests will be used to compare means of primary outcome responses between participants in the DP and placebo arms. The effect estimate will be presented as a mean difference in the responses reported with 95% confidence intervals and p values. There will be no adjustment for confounders. For each of the primary outcomes, we will investigate adjusting for the corresponding measure at baseline. Subgroup analyses by sex for all the primary outcome measures will be conducted and unpaired t tests will be used to compare

mean responses in each group, with interaction terms fitted to assess whether effects of the intervention on outcomes differ between subgroups.

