### 5.5.2. Comparison of primary outcome responses between trial arms

Table 3: Differences in responses between DP and Placebo arms at week 8 for BCG, YF-17D, Ty21a, HPV and week 52 for Td.

	DP	Placebo			
Vaccine	Mean (SD)**	Mean (SD)**	Mean difference***	95% CI	P value*
BCG					
YF-17D					
Ty21a					
HPV					
Td					

\*P values reported from unpaired t test

\*\* If data are not normally distributed, median (IQR) or geometric mean (SD) will be presented

\*\*\* If data not normally distributed, Geometric Mean Ratios (GMR) will be presented

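### The primary comparison is an unadjusted t test with baseline adjustment only to be investigated: valid, but it forgoes precision that an underpowered trial could have at almost no cost

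*SAP*

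**What the plan says.** Section 5.2.1 of the SAP names the primary test: "Unpaired t tests will be used to compare means of primary outcome responses between participants in the DP and placebo arms". It then rules out covariates in general and leaves the baseline value open: "There will be no adjustment for confounders. For each of the primary outcomes, we will investigate adjusting for the corresponding measure at baseline". No model is written down for that adjustment, and its role beside the t test is not stated.

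The Table 3 shell in Section 5.5.2 has one P value column, with the footnote "P values reported from unpaired t test". Section 3.1 sets two-sided tests at the 5% level.

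Section 2.2 reports that, because of COVID-19 restrictions, "it was not possible to achieve the original target sample size". Table 1 then gives power for the 341 participants enrolled. The primary population is those infected with malaria at baseline: 102 per arm, or 82 per arm after 20% loss to follow-up.

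**The concern.** In a randomised comparison, adjusting for the baseline value of the outcome is not confounder control. It removes between-participant variation that was present before treatment, and so narrows the confidence interval for the same effect. The sentence ruling out confounder adjustment is therefore no reason to leave it out.

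The SAP expects to have a baseline measure for each primary outcome, since it proposes to look at adjusting for it, yet the reported estimate ignores it. At stake is power in a trial that has just over half its intended participants and draws its primary population from a subset of them.

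**Working it through.** **Inputs.** From Section 2.2: 341 enrolled, 60% prevalence, 20% loss, SD 0.3 to 0.6 and differences 0.10 to 0.20 on the log10 scale. From Section 2.1: 1:1 allocation. From Section 3.1: two-sided 5%. The correlation rho between the baseline and outcome values of the same measure is not in the SAP. It is assumed here over 0 to 0.7.

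**Step 1: size of the primary population.** 341 × 0.6 / 2 = 102.3 per arm; 102.3 × 0.8 = 81.8, or 82 per arm. This agrees with Table 1. It is a planning figure, not a count.

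**Step 2: reproduce Table 1.** Power of the two-sample t test with n = 82 per arm comes from the noncentral t distribution with 162 degrees of freedom and noncentrality difference / (SD × √(2/82)). For SD 0.4 and difference 0.16 the noncentrality is 0.16 / (0.4 × 0.1562) = 2.56 and power is 72.1%; Table 1 gives 72%. All 24 cells reproduce to within 1 point, so Table 1 describes the unadjusted test. The cells above 80% are four at SD 0.3 (84%, 92%, 97%, 99%) and two at SD 0.4 (82%, 89%): 6 of 24.

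**Step 3: adjust for baseline.** In a linear regression on arm and baseline, the residual SD is SD × √(1 − rho²). The equivalent unadjusted sample size is 82 / (1 − rho²) per arm. With SD 0.4 and difference 0.16:

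| rho | residual SD | equivalent n per arm | power | Table 1 cells above 80% |
|---|---|---|---|---|
| 0 | 0.400 | 82 | 72% | 6 |
| 0.2 | 0.392 | 85 | 74% | 6 |
| 0.3 | 0.382 | 90 | 76% | 6 |
| 0.4 | 0.367 | 98 | 79% | 6 |
| 0.5 | 0.346 | 109 | 84% | 9 |
| 0.7 | 0.286 | 161 | 95% | 14 |

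The covariate costs one degree of freedom, 161 in place of 162. That moves the two-sided 5% critical value from 1.9747 to 1.9748 and changes no figure in the table.

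**Step 4: scale against the shortfall.** The proportion of the target reached is 341 / 640 = 0.533. Recovering all the lost precision would need 1 − rho² = 0.533, so rho = √0.467 = 0.68.

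**The case against.** The strongest reply is that nothing here is wrong. The unpaired t test is valid and unbiased under randomisation, and Table 1 gives the power of that same test, so design and analysis agree. That stands, and it limits the point to efficiency.

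A reader might infer that the plan yields two competing results per vaccine with no rule for choosing, and so an inflated false-positive rate. If the smaller of the two P values were always reported, simulation (20,000 runs per correlation, 82 per arm) puts the error at about 6.1% for rho 0.2 and 8.4% for rho 0.7. The SAP does not permit that choice. Section 5.2.1 names the t test as the comparison, and the Table 3 footnote fixes it as the source of the P value. What is left is an adjusted analysis with no stated model or role.

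The benefit is also uncertain. No correlation is documented, it may differ across the five vaccines, and no further Table 1 cell passes 80% at rho 0.3 or 0.4. Gains may be negligible for an outcome such as the response to a priming HPV dose if baseline antibody is uniformly low.

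Finally, it cannot be taken as known that every baseline assay has been done. Section 5.2.1 implies a baseline measure for each outcome, and seroconversion for Ty21a would ordinarily need one. But Section 2.7 gives no time point for a baseline vaccine response, and the Table 2 shell lists none.

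**Conclusion.** The point holds as an efficiency weakness that should be corrected; it is not an error in the plan. For the 72% cell, power with a pre-specified baseline covariate would be 76%, 84% or 95% at rho 0.3, 0.5 or 0.7. The gain is small below about 0.3, useful from about 0.4 to 0.5, and close to making good the recruitment shortfall only near 0.7. Where baseline carries no information there is about no gain, and one degree of freedom is lost.

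These figures assume 82 per arm, a linear relation between baseline and outcome on the analysis scale, and a baseline taken before treatment. Because the cost is so low, the recommendation does not depend on knowing rho, but the size of the benefit does.

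**What to change.** Before unblinding, amend the SAP as follows.

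- **Section 5.2.1.** For each antigen with a pre-treatment baseline measurement, make the primary estimate a linear regression of the response on arm plus the baseline value of the same measure. Use the log10 scale where Checking assumptions leads to log transformation. Keep the unadjusted t test (or the Wilcoxon test if normality fails) as the sensitivity analysis, and as the primary analysis for any antigen without a baseline assay. List which antigens fall in each group.
- **Definition of baseline.** Use the sample taken before the first DP or placebo dose. This matters most for Td, given at week 28, where a sample taken just before vaccination could already reflect the allocated treatment.
- **Section 5.3.** It currently excludes all imputation. Allow a simple fill or a missing indicator for a missing baseline covariate only, so that no participant with an outcome is dropped. Outcomes stay unimputed.
- **Checking assumptions and Table 3.** Apply the normality and equal-variance checks to the regression residuals, and change the footnote so that the P value comes from the regression.

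The cost is wording in these places. No participants are added. Laboratory work is needed only if the sponsor chooses to run a baseline assay not yet done, and the fallback above makes that optional.
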